## 17.1. ADVERSE EVENTS

Adverse events will be coded to SOC and PT using the MedDRA dictionary (version 18.0) and will be classified as follows:

- **Prior AEs** are defined as AEs that started on or after the signature of the informed consent but prior to the first dose of study drug (i.e., first dose in Period 1) and have not worsened in severity on or after the first dose of study drug;
- **Treatment-emergent adverse events (TEAEs)** are defined as any AEs that started or worsened in severity on or after the first dose of study drug;

Only TEAEs will be summarized; listings will include all AEs (see APPENDIX 1 for handling of partial dates for AEs). AEs will be reported under the treatment group being received when AE first occurs/worsens. Should an AE with a partially missing onset date can be assigned to more than one treatment group, it will be reported under the active treatment group with the lowest dose. For TEAEs that started during the safety follow-up period, TEAEs will be attributed to the last treatment group received in the study.

An overall summary of number and percentage of subjects within each of the categories described in the following subsections (e.g., all TEAEs, SAEs, AEs leading to discontinuation of study drug, etc.) will be provided. A similar overall summary will be presented for the subset of TEAEs that started during the safety follow-up period.

For TEAEs summarized by SOC and PT, SOC will be sorted in alphabetical order and the PTs within each SOC will be sorted in descending frequency order for the pooled JZP-110 treatment group. For PT only tables, incidence will be sorted similarly to the PTs in the summaries by SOC and PT.

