### 3.2 Rationale for Study Design and Control Group

This study was designed to be consistent with the US FDA Guidance for Industry on Providing Clinical Evidence of Effectiveness for Human Drug and Biological Products, with the ICH, Guidance on The Extent of Population Exposure to Assess Clinical Safety for Drugs Intended for Long-Term Treatment of Non-Life-Threatening Conditions and with the ethical principles given in these guidances, which have their origins in the Declaration of Helsinki. The inclusion of a placebo as a control into sequences A and B in the Treatment Phase of this study is necessary to determine the efficacy and safety of this new investigational medicinal product. Inclusion of the placebo sequence C will preserve blinding. A crossover design has been selected in order to evaluate the safety, tolerability, and effects on excessive sleepiness across a range of doses. Phase 2 studies in patients with narcolepsy have shown that JZP-110 (150 and 300 mg doses) improves subjective and objective parameters of sleepiness and is well tolerated. While the same sleepiness parameters are included as endpoints in this study as in the Phase 2 narcolepsy study, the objective MWT assessment was made optional in Amendment 2 for this study as unlike in narcolepsy, it is not a common assessment for diagnosing sleepiness in PD and it has not been validated in this patient population. The Phase 2a narcolepsy study was a crossover design and a carryover effect was not observed. In light of this and the short half-life of JZP-110, a placebo washout between each treatment period was not included. The doses of 75, 150 and 300 mg selected for evaluation in this study are comparable to those currently being evaluated in ongoing Phase 3 studies in the OSA and narcolepsy populations. It is feasible that lower doses may be pharmacologically active and therefore, a broad range of doses from 75 to 300 mg given once daily for 7 days

was selected for evaluation and will provide useful data to inform dose selection for subsequent studies.

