## **9.13 Safety Analysis**

### **9.13.1 Adverse Events**

Adverse events will be coded using the Medical Dictionary for Regulatory Activities system to classify events under primary system organ class and preferred term. The number and percent of subjects who experienced TEAEs, TEAEs related to study drug, or SAEs; who died during the study; or who discontinued study drug or withdrew from the study due to an AE will be summarized by treatment at onset. Results will be presented by system organ class, and preferred term.

A TEAE is defined as an AE that either began after first study drug dose or worsened after the first dose. When determining the percent of subjects who experience an AE, multiple increases in severity are only counted as one AE. For example, a subject who develops a mild headache after the first study drug dose (that was not present during screening or at baseline), which subsequently worsens to moderate, then severe, is only counted once under the preferred term of headache.

For all AE summaries, if a subject has more than one AE within a preferred term on a given dose, the subject is counted only once at the maximum severity and with the closest relationship to study drug. If a subject has more than one AE within a system organ class, the subject is similarly counted once when reporting results for that system organ class.

All AE data will be listed.

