**Table 1 Overview of Study Treatment Sequences by Treatment Period**

Treatment Sequence	Period 1	Period 2	Period 3	Period 4
	Week 1	Week 2	Week 3	Week 4
A (n=21)	Placebo	JZP-110 75 mg	JZP-110 150 mg	JZP-110 300 mg
B (n=21)	JZP-110 75 mg	JZP-110 150 mg	JZP-110 300 mg	Placebo
C (n=7)	Placebo	Placebo	Placebo	Placebo

[figure not shown]
During the first 6 days of each treatment period, subjects will take once-daily, oral doses of study drug (75, 150, or 300 mg JZP-110, or placebo) with water at home.

On the last day of each treatment period (i.e., Days 7, 14, 21, and 28), subjects will take their usual PD medications and sleep medications allowed by the protocol as per their usual schedule, and return to the study center where they will take their dose of study drug for that day and undergo assessments for efficacy and safety and tolerability (Visits 3, 4, 5, and 6; see Section 3.5 for the complete schedule of events). Pending the investigator's assessment of safety and tolerability, subjects will proceed to the next treatment period. Subjects will receive their last dose of study drug at Visit 6 (Day 28) prior to the Week 4 visit assessments. Subjects will return for a Safety Follow-up visit (Visit 7) approximately 7 days after the last dose of study drug for follow-up safety assessments. Unless there are outstanding safety issues that require additional follow-up, subjects will be discharged from the study at the Safety Follow-up visit (Visit 7).

The schema of the study is represented in Figure 1.

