### 13. PRIOR AND CONCOMITANT MEDICATIONS

Medications will be coded using the World Health Organization (WHO) drug dictionary, version March 2015E and will be classified as follows (see APPENDIX 1 for handling of partial dates for medications.):

- **Prior medications** are defined as any medications that were started prior to the first dose of study drug
- **Concomitant medications** are defined as any medications that were taken on or after the day the first dose of study drug was taken

Prior and concomitant medications will be further classified as follows:

- PD motor functions-related medications are defined as those medications taken for the treatment of PD motor function symptoms.
- Sleep promoting medications are defined as trazodone, benzodiazepines, nonbenzodiazepines (e.g. zolpidem, zaleplon, or eszopiclone), suvorexant, melatonin receptor agonists, GABA receptor agonists opioids, and skeletal muscle relaxants (e.g. baclofen).
- Other medications will be defined as all medications other than PD motor functions and sleep promoting medications.

PD motor functions-related concomitant medications, sleep promoting concomitant medications and other concomitant medications will be summarized separately by anatomical therapeutic class (ATC) level 3 and preferred drug name based on the SAF by treatment group (including all JZP-110 doses pooled into one group) and broken down further by sequence for the placebo treatment group. A medication will be accounted once for each treatment group/sequence during which the medication was taken.

Prior medications will be provided in subject data listings only.

Number and percentage of subjects using a primary therapy device for OSA at Baseline will be summarized based on the SAF by treatment group (including all JZP-110 doses pooled into one group) and broken down further by sequence for the placebo treatment group. For subjects who used a primary therapy device for OSA at Baseline, number and percentage of subjects who have been stable on their primary therapy device settings for at least 4 weeks prior to the Baseline visit as well as if they demonstrated adequate compliance on their OSA device during the same period will be summarized similarly. Number and percentage of subjects who demonstrated adequate compliance with OSA therapy since last visit will be also provided similarly based on the SAF for each post-Baseline visit.

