### 17. SAFETY OUTCOMES

All outputs for safety outcomes will be based on the SAF and, unless otherwise specified, presented by treatment group (JZP-110 75 mg, JZP-110 150 mg, JZP-110 300 mg, and placebo), regardless of the sequence and period. Summaries will also be presented for the pooled JZP-110 treatment groups, when applicable (i.e., incidences and shifts from Baseline), as well as by sequence for Placebo, but regardless of the period.

For subjects who received Sequence C, the following rules will be followed to compute the descriptive statistics, incidences and shifts from Baseline:

- For descriptive statistics, the average of the non-missing values collected at the end of each treatment period will be used;
- For incidences, each subject will be counted only once for each category;
- For shifts from Baseline, the worst value among the non-missing values collected at the end of each treatment period will be used.

For the summaries on the pooled JZP-110 group, the same rules than for the subjects who received Sequence C will be followed for the incidences and shifts from Baseline.

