### **17.1.4. TEAEs LEADING TO DISCONTINUATION OF STUDY DRUG AND/OR TO WITHDRAWAL FROM STUDY**

The incidence of TEAEs leading to permanent discontinuation of study drug and/or to withdrawal from study will be summarized together by SOC and PT. Generally, only one AE has an action taken of 'drug withdrawn' corresponding to subject's primary reason for discontinuation from study drug due to an AE. In the event that more than one AE has an action taken of 'drug withdrawn' for a subject, subject will count only once within a SOC or PT.

A listing including all TEAEs leading to permanent discontinuation of study drug and/or to withdrawal from study will be provided.

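### The AE tables place persisting events, and discontinuations due to them, under the dose at onset or worsening; with a fixed 75-150-300 mg order this can understate AEs at the higher doses

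*SAP*

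**What the plan says.** SAP 17.1 attributes events by dose: "AEs will be reported under the treatment group being received when AE first occurs/worsens". Protocol 9.13.1 names onset alone. Its sentence covers TEAEs, SAEs and deaths, and ends with subjects "or who discontinued study drug or withdrew from the study due to an AE will be summarized by treatment at onset".

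SAP 17.1.4 says: "The incidence of TEAEs leading to permanent discontinuation of study drug and/or to withdrawal from study will be summarized together by SOC and PT". It adds a listing but no rule on which dose column to use, so the rule in 17.1 applies. Under SAP 17, safety outputs are "presented by treatment group (JZP-110 75 mg, JZP-110 150 mg, JZP-110 300 mg, and placebo), regardless of the sequence and period". A pooled JZP-110 column is also planned for incidences.

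The dose order never varies. In SAP Table 1, Sequence B reads "JZP-110 75 mg JZP-110 150 mg JZP-110 300 mg Placebo", and Sequence A has the same ascent after a placebo week. Protocol 3.2 states that "a placebo washout between each treatment period was not included".

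Three further rules matter:
- SAP 17.1 sends an AE whose partial onset date fits several treatments to the lowest active dose.
- Protocol 9.13.1 counts repeated increases in severity as one AE.
- SAP 13 uses on-treatment counting for concomitant medications: "A medication will be accounted once for each treatment group/sequence during which the medication was taken".

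**The concern.** If dose order varied between subjects, events carried from one period to the next would be credited to different doses. Here, among the active doses, an event that persists unchanged can only be credited to a lower dose than the one being taken. The subject remains in the 150 and 300 mg denominators and looks event-free there, although a new onset of an ongoing event is not possible.

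Discontinuations follow the same rule. An event that begins at 75 mg, continues unchanged and leads to stopping at 300 mg enters the SOC/PT discontinuation table under a dose the subject had already completed. The rule for partial onset dates pushes in the same direction.

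Safety and tolerability is the primary objective, and Protocol 3.2 says the dose range is meant to help choose doses for later studies. No planned AE table shows what subjects experienced while taking each dose.

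**Working it through.** The plan states no AE rate, so there is no figure of its own to reproduce. The check has three parts.

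**1. One subject followed through the tables.** Take a Sequence B subject whose event starts in Period 1 (75 mg), continues unchanged, and leads to stopping in Period 3 (300 mg).
- TEAE table (SAP 17.1.1): counted at 75 mg, not at 150 or 300 mg.
- Discontinuation table (SAP 17.1.4): counted at 75 mg.
- Disposition (SAP 9): withdrawal in Period 3 of Sequence B, which is 300 mg.

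**2. Counting model.** From the documents: expected active subjects are 49 × 3/7 = 21 in each of Sequences A and B, so 42; the order is 75, 150, 300 mg. Assumed: no dropout; p_k is the onset probability at dose k in subjects with no ongoing event; q is the probability that an event persists into the next dose; w is the probability that a persisting event worsens there and is counted again.

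- Carried over: c_k = q × P_(k−1), with c = 0 at 75 mg
- New: n_k = (1 − c_k) × p_k
- Planned count: n_k + w × c_k
- Present on dose: P_k = c_k + n_k

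Worked example with p = 15% at each dose, q = 0.9, w = 0:
- 150 mg: c = 0.9 × 0.15 = 0.135; n = 0.865 × 0.15 = 0.130; P = 0.265.
- 300 mg: c = 0.9 × 0.26475 = 0.238; n = 0.762 × 0.15 = 0.114; P = 0.353.

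In 42 subjects the 300 mg column would show 4.8 where 14.8 have an event present.

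| Assumed onset %, 75/150/300 mg | q | w | Planned count % | Present on dose % |
|---|---|---|---|---|
| 15/15/15 | 0 | 0 | 15.0/15.0/15.0 | 15.0/15.0/15.0 |
| 15/15/15 | 0.5 | 0 | 15.0/13.9/13.4 | 15.0/21.4/24.1 |
| 15/15/15 | 0.9 | 0 | 15.0/13.0/11.4 | 15.0/26.5/35.3 |
| 15/15/15 | 0.9 | 0.3 | 15.0/17.0/18.6 | 15.0/26.5/35.3 |
| 10/20/30 | 0.9 | 0 | 10.0/18.2/22.7 | 10.0/27.2/47.1 |
| 10/20/30 | 0.9 | 0.3 | 10.0/20.9/30.0 | 10.0/27.2/47.1 |

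**3. Full persistence, no worsening.** The planned count is the on-dose percentage minus that at the previous dose:
- 10/20/30 on dose is tabulated as 10/10/10 (flat).
- 10/30/60 is tabulated as 10/20/30 (still rising).
- 20/25/28 is tabulated as 20/5/3 (falling).

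The direction is consistent, but the shape depends on the unknown rates. The equal-onset rows also carry a warning: on-dose prevalence climbs from 15.0% to 35.3% although dose has no effect on onset.

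**The case against.** The strongest case against has five parts.

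- **The higher-dose columns are not emptied.** Under the SAP, an event that worsens at a higher dose is reported there. Protocol 9.13.1 counts a subject once per preferred term on a given dose, so a recurrence recorded as a new AE counts again. Only continuous events of unchanged severity are missed. This stands. A reader might infer that tolerability must look flat across doses; part 3 of the working shows that this is only one possible outcome.
- **The dose at withdrawal can be found.** A reader might infer that AE discontinuations are visible only by onset dose. SAP 9 tabulates withdrawal by sequence and period with reason, and sequence plus period fixes the dose (300 mg is Period 4 in A and Period 3 in B). SAP 6 puts sequence and dose received in the listings, and SAP 17.1.4 lists every TEAE leading to discontinuation. This mitigates the problem, but the reader must combine different periods across sequences, and none of it is a SOC/PT table by dose at withdrawal.
- **Persistence may be limited.** The investigator reviews safety before each escalation, and early termination is considered for subjects who do not tolerate the drug. This is fair, and the documents give no rate either way.
- **On-dose counting has its own bias.** A reader might want dose comparisons based on the on-dose table. In a fixed order prevalence accumulates with time. Overlap counting would also carry placebo-onset events in Sequence A into the active columns, and 300 mg events in Sequence B into the placebo column. This stands, so that table can only be a supplement.
- **Safety is descriptive.** No inference is planned, and the pooled column, vital signs and ECG summaries are unaffected. This is true, but none of these tabulates AEs by the dose being taken.

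The medication rule in SAP 13 counts exposure rather than the incidence of an outcome. It shows that such counting is feasible, not that the SAP contradicts itself.

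**Conclusion.** The concern holds for the AE tables. With a fixed ascending order and no washout, attribution to onset or worsening leaves unchanged persisting events out of the higher-dose columns, and can place a discontinuation under a completed dose. The gradient is attenuated by an amount the documents do not allow one to fix. Under the assumed rates with 90% persistence and no re-counting, the 300 mg column shows 11.4% against 35.3%, or 22.7% against 47.1%. The loss is nil when events resolve before the next dose, and smaller when worsened events count again.

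The worsening rule is itself unclear. The SAP does not say whether an AE that starts at 75 mg and worsens at 300 mg enters one column or both. The protocol points to onset, and SAP 3.6 does not list the difference as a change.

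This is an inexpensive improvement to reporting on the primary objective and should be made. It does not make the onset table wrong as a count of new events.

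**What to change.** 1. **SAP 17.1.4:** tabulate TEAEs leading to discontinuation by the treatment at last dose. Keep the onset treatment in the listing or in a parallel column.
2. **SAP 17.1.1:** keep the onset table. Add a supplementary SOC/PT table of TEAEs present during each treatment, split into new onset and ongoing from an earlier treatment, with events that began on placebo shown separately. State a rule for partial stop dates: Appendix 1 imputes the latest possible date, which would stretch events into later doses, and SAP 7.2 confines imputed dates to classification.
3. **SAP 17.1:** state whether an AE that worsens at a higher dose counts in both columns, and list any departure from the protocol in SAP 3.6.

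A footnote should say that the onset and on-dose tables are to be read together, and that the on-dose table alone does not support dose comparisons because prevalence accumulates in a fixed order.

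The cost is SAP wording, some programming and one added table, from dates already collected. A persisting event will appear in more than one column, so the columns will not add up.

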## 3. STUDY DESIGN

### 3.1. GENERAL DESCRIPTION

This is a 4-week, multicenter, randomized, double-blind, placebo controlled, ascending dose, 4-period crossover study designed to evaluate the safety, tolerability, efficacy, and PK of JZP-110 (75, 150, and 300 mg) in the treatment of excessive sleepiness in adult subjects with idiopathic PD. Depending on study center capabilities, subjects will have the option of enrolling into 1 of 2 groups: Group 1 and Group 2. Subjects enrolled in Group 1 will undergo both objective (MWT) and subjective (ESS) assessments of sleepiness. Subjects enrolled in Group 2 will undergo only the subjective (ESS) assessment of sleepiness. Following completion of the Screening and Baseline visits, approximately 49 eligible subjects will be randomly assigned (3:3:1) to 1 of 3 treatment sequences in order to have approximately

34 subjects complete Treatment Sequences A and B, and 6 subjects complete Treatment Sequence C (Table 1). There will be no stratification based on group.

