### PRESENTATION OF TREATMENT GROUPS

For outputs where Treatment Sequence will be represented, sequence will be presented as follows and in the order indicated:

Treatment Sequence	For Tables, Figures, and Listings
Sequence A	Placebo/JZP-110 75mg/JZP-110 150mg/ JZP-110 300mg
Sequence B	JZP-110 75mg/JZP-110 150mg/ JZP-110 300mg/Placebo
Sequence C	Placebo/Placebo/Placebo/Placebo

For outputs where treatment groups will be represented, group will be presented as follows and in the order indicated:

Treatment Group	For Tables, Figures, and Listings
JZP-110 75 mg	JZP-110 75 mg
JZP-110 150 mg	JZP-110 150 mg
JZP-110 300 mg	JZP-110 300 mg
JZP-110 pooled	JZP-110 Pooled
Placebo	Placebo

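### Adverse events whose partial onset date fits several treatments are counted under the lowest active dose, which on net shifts them from 150 and 300 mg to 75 mg

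*SAP*

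**What the plan says.** The default in SAP 17.1 is that "AEs will be reported under the treatment group being received when AE first occurs/worsens". This matches Protocol 9.13.1, under which adverse events "will be summarized by treatment at onset". The protocol has no rule for incomplete onset dates. The SAP adds one: "Should an AE with a partially missing onset date can be assigned to more than one treatment group", then "it will be reported under the active treatment group with the lowest dose".

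SAP 3.1 describes an "ascending dose, 4-period crossover study". The order of treatments, from SAP Appendix 2, is:

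- Sequence A: "Placebo/JZP-110 75mg/JZP-110 150mg/ JZP-110 300mg"
- Sequence B: "JZP-110 75mg/JZP-110 150mg/ JZP-110 300mg/Placebo"

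Periods last 7 days and end on Days 7, 14, 21 and 28. Protocol 3.2 states that there is no placebo washout between them. SAP Appendix 1 uses partial dates only to decide whether an event is treatment-emergent, not which dose it belongs to. No analysis under another dose attribution is planned.

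**The concern.** The rule makes two choices. Preferring an active treatment over placebo is cautious. Preferring the lowest active dose is not cautious for 150 and 300 mg. Because the doses always ascend, the lowest compatible dose is also the earliest active one, so the errors do not cancel between doses.

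The choice also runs against the SAP's other conventions, which settle ambiguity towards the worse reading:

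- the worst value for shifts in subjects on Sequence C and in the pooled group (SAP 17);
- the greatest severity (17.1.1.1);
- the closest relationship to study drug (17.1.1.2);
- an event with both dates missing is assumed to be treatment-emergent (Appendix 1).

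Safety and tolerability is the primary objective, and Protocol 9.2 plans no inferential statistics for it. The descriptive tables by dose are therefore the primary result, and Protocol 3.2 expects the dose range to inform later dose selection.

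**Working it through.** The documents state no figure for this rule, so there is none to reproduce.

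**Inputs.** Attribution rule: SAP 17.1. Order of treatments: SAP Table 1 and Appendix 2. Randomized to A and B: 21 + 21 = 42; planned completers in A and B: 34 (SAP 3.4). Share of events with a partial onset date: not given, so assumed at 5%, 10% and 20%. Sequence C has only placebo and can never be ambiguous.

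**Step 1: every ambiguous window.** A partial date that fits more than one treatment spans two or more adjacent periods. There are six such windows in each sequence.

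| Sequence | Window | SAP rule | Highest active dose |
|---|---|---|---|
| A | placebo, 75 | 75 | 75 |
| A | placebo, 75, 150 | 75 | 150 |
| A | placebo, 75, 150, 300 | 75 | 300 |
| A | 75, 150 | 75 | 150 |
| A | 75, 150, 300 | 75 | 300 |
| A | 150, 300 | 150 | 300 |
| B | 75, 150 | 75 | 150 |
| B | 75, 150, 300 | 75 | 300 |
| B | 75, 150, 300, placebo | 75 | 300 |
| B | 150, 300 | 150 | 300 |
| B | 150, 300, placebo | 150 | 300 |
| B | 300, placebo | 300 | 300 |

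Under the SAP rule, 8 of the 12 windows go to 75 mg, 3 to 150 mg, 1 to 300 mg and none to placebo. Of the 8 windows that include 300 mg, 7 are sent lower. Of the 10 that include 150 mg, 7 are sent to 75 mg. The highest-dose rule gives the mirror image: 1, 3 and 8 windows to 75, 150 and 300 mg.

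**Step 2: effect of one subject.** 1/42 = 2.4 percentage points; 1/34 = 2.9 percentage points. This is an upper limit, because a subject counts once per term within a dose.

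**Step 3: illustration with the day missing and the month known.** Assume onset is uniform over the 28 treatment days, average over 365 start dates, weight A and B equally, and use no stop date or visit information. Events with a missing day are then tabulated as follows:

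| True treatment | Placebo | 75 mg | 150 mg | 300 mg |
|---|---|---|---|---|
| Placebo | 13.2% | 63.8% | 11.5% | 11.5% |
| 75 mg | 0 | 100% | 0 | 0 |
| 150 mg | 0 | 86.8% | 13.2% | 0 |
| 300 mg | 0 | 63.8% | 23.0% | 13.2% |

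**Step 4: effect on all events.** With a share f of partial dates, tabulated count = (1 − f) × true count + f × (true counts redistributed as in step 3). Take assumed true counts of 8, 8, 12 and 20 for placebo, 75, 150 and 300 mg. At f = 0.20 the 75 mg count is 0.8 × 8 + 0.2 × (8 × 0.638 + 8 + 12 × 0.868 + 20 × 0.638) = 6.4 + 0.2 × 36.28 = 13.7.

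| f | Placebo | 75 mg | 150 mg | 300 mg |
|---|---|---|---|---|
| 0 | 8 | 8 | 12 | 20 |
| 5% | 7.7 | 9.4 | 11.8 | 19.2 |
| 10% | 7.3 | 10.8 | 11.5 | 18.4 |
| 20% | 6.6 | 13.7 | 11.0 | 16.7 |

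The gradient across active doses flattens in every row.

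**The case against.** The strongest objection is that no attribution between doses is conservative for every dose. A highest-dose rule removes events from 75 mg, makes the lowest dose look cleaner and steepens the apparent dose-response. The SAP rule is prespecified and protects the comparison of active with placebo. This stands: the alternative is also biased, and its cost has to be stated.

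The second objection is that few events may be affected. Adverse events are recorded at weekly visits (Protocol 7.2.2 and 7.3.2), data pass programmed and manual checks (Protocol 10), and known stop dates can narrow the window. This also stands. The percentages in step 3 belong to a model that ignores such information; they are not properties of the trial.

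The third objection is that the harm is visible. All adverse events are listed, imputed dates are kept out of the listings (SAP 7.2), and serious events and those leading to discontinuation have their own listings. A reader could reassign events by hand, but no planned table would show the result.

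Three stronger readings are tempting, and the documents do not support them:

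- A reader might infer that every ambiguous event moves down. It does not: in Sequence B, the window of 300 mg and placebo goes to 300 mg, and 150 mg gains some events from 300 mg and placebo. Only the net direction is down.
- A reader might infer that the rule inverts the dose-response. In the illustration the order of the active doses holds at 5% and 10%. Only at an assumed 20% does 75 mg pass 150 mg, and 300 mg stays highest.
- A reader might infer that each reassigned event lowers the higher dose and raises 75 mg by 2.4 points. Dropout changes the denominator, and another event with the same term at either dose can leave that dose's figure unchanged.

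**Conclusion.** The point holds as a minor one. The net shift from 150 and 300 mg to 75 mg follows from the rule and the fixed dose order, and the flattening affects the descriptive tables that carry the primary objective. Nothing else in the plan corrects the dose attribution.

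The total size is unknown because the documents do not give the number of partial dates; with weekly visits it is probably small. For each affected subject, the change in a dose's incidence for a term is at most about 2.4 to 2.9 percentage points, and it arises only if the subject has no other event with that term at the dose concerned. The range assumes that between 34 and 42 subjects are exposed at a dose. The comparison of active with placebo errs in the cautious direction. The pooled JZP-110 column is unaffected by moves between active doses, although it gains events from placebo.

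**What to change.** Make one of two changes in SAP 17.1 before unblinding:

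- assign these events to the highest active dose compatible with the known parts of the date; or
- keep the current rule and repeat the by-dose TEAE incidence table under the highest-dose attribution.

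In either case, footnote the number of events affected. The second option is the more informative. For events that began on an active dose, the two tables bracket the incidence at 75 mg and at 300 mg. They do not strictly bracket 150 mg, because an event that fits all three doses goes to 75 mg in one table and to 300 mg in the other.

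The cost is one programming rule or one extra table. The downside is that the highest-dose attribution may overstate incidence at the higher doses and understate it at 75 mg. If the footnoted number is close to zero, the two tables will hardly differ.
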